8.2 Other Assessments

Levels of TG2 in plasma will be collected for exploratory assessment.

9. SAFETY ASSESSMENTS

9.1 Safety Variables

Safety and tolerability will be assessed through the monitoring of the following:

- AEs and adverse drug reactions (ADRs)
- Vital signs (systolic and diastolic blood pressure, pulse rate, respiratory rate, and body temperature)
- Oxygen saturation measured via pulse oximetry
- 12-lead ECGs (heart rate, PR, QRS, and QTcF)
- Clinical laboratory evaluations: clinical chemistry (including fasting glucose) and haematology
- Physical examinations
- Spirometry (FEV₁, FVC, FEV₁ % of predicted normal and lower limit of normal value, FVC % of predicted normal and lower limit of normal value, and FEV₁/FVC ratio)
- Diffusing capacity (D_{LCO} [unadjusted], D_{LCO} % predicted, D_{LCO} corrected for haemoglobin, D_{LCO} corrected for haemoglobin % predicted, KCO, and VA)
- ADAs and nAb
- Analysis of systemic markers* of immediate hypersensitivity reactions pre-dose and post-dose (post-dose only if required) including:
 - markers of cytokine release syndrome (IFN- γ , TNF- α , IL-1 β , IL-2, IL-4, IL-6, IL-8, IL-10, IL-12 (p70), and IL-13)
 - mast cell tryptase
 - complement markers (C3a, C5a, CH50, and SC5b-9)
 - CHF10067 IgE.

*During the study, the markers analysed may be adjusted as required. Any adjustment will be with consideration for subject safety and operational activities.

Clinical Study Code No.: CLI-10067AA1-01	Version No.: 6.0
EUDRACT No.: 2022-001079-15	Date: 06 July 2023

9.2 Emergency Situation

In case of health emergency, including COVID-19, the Investigator/site staff must take all necessary precautions to minimise and avoid the risk of transmission and exposure to study subjects and site staff, according to local guidelines. In that particular case:

- a time window for study visits could be allowed when subjects are not able to arrive to the site or to attend the visit
- onsite study visits could be cancelled or replaced by phone calls, or some assessments could be missed.

Special case of COVID-19 outbreak:

Every effort should be made by the site to confirm all suspected incidences of COVID-19 in accordance with local diagnostic guidelines. Documentation of testing and results obtained outside the clinical site, should be collected within 14 days of confirmed diagnosis (or whenever possible) and recorded in the eCRF.

All incidences of COVID-19 as well as the impact on study visits and subject completion must be captured in the eCRF.

Occurrence of SARS-CoV-2 infection and/or COVID-19 disease during the study does not automatically lead to withdrawal of the subject. It will be up to the Investigator's judgement to withdraw the subject from the study if he/she deems that remaining in the study will place the subject and/or the clinical site at undue risk by continuing their participation. All efforts should be made to keep the subject on study drug, if possible.

In case study visits or procedures are modified or missed due to COVID-19, the relevant information will be recorded in the eCRF.

As of the date of this protocol version, there is no specific treatment for COVID-19 and several vaccine therapies have been developed and approved by health authorities with vaccination campaigning being initiated worldwide. For all confirmed cases of COVID-19/SARS-CoV-2 the Investigator must follow the standard of care in accordance with local treatment guidelines. All concomitant treatments must be recorded in the eCRF.

In case of COVID-19 suspect, Investigators are encouraged to perform diagnostic testing locally or obtain results of tests from hospital where the event was diagnosed and/or managed, and every effort should be made to complete the assessments required by the current local guidelines for COVID-19 management (e.g., SARS-CoV-2 test, chest imaging) and to guarantee the appropriate management.

Clinical Study Code No.: CLI-10067AA1-01	Version No.: 6.0
EUDRACT No.: 2022-001079-15	Date: 06 July 2023

10. ADVERSE EVENT REPORTING

10.1 Definitions

An **Adverse Event** is “any untoward medical occurrence in a patient or clinical study subject administered a medicinal product and which does not necessarily have a causal relationship with this treatment”.

An AE can therefore be any unfavourable and unintended sign (including abnormal laboratory finding), symptom, or disease temporally associated with the use of a medicinal product, whether or not considered related to the medicinal product.

An **Adverse Drug Reaction** is an “untoward and unintended responses to an investigational medicinal product related to any dose administered”.

All AEs judged by either the reporting Investigator or the Sponsor as having a reasonable causal relationship to a medicinal product qualify as adverse reactions. The expression “reasonable causal relationship” means to convey in general that there are facts (evidence) or arguments meant to suggest a causal relationship.

The definition covers also medication errors and uses outside what is foreseen in the protocol, including misuse and abuse of the product.

A **Serious Adverse Event (SAE)/Serious Adverse Drug Reaction** is any untoward medical occurrence or effect that at any dose falls in one or more of the following categories:

- **Results in death**

Death is not an AE but an outcome. It is the cause of death that should be regarded as the AE. The only exception to this rule is “sudden death” where no cause has been established; in this latter instance, “sudden death” should be regarded as the AE and “fatal” as its reason for being serious.

- **Is life-threatening**

Life-threatening refers to an event in which the subject was at risk of death at the time of the event (e.g., aplastic anaemia, acute renal failure, and anaphylaxis). The term does not refer to an event which hypothetically might have caused death if it were more severe.

- **Requires hospitalisation or prolongation of existing hospitalisation**

Hospitalisation refers to a situation whereby an AE is associated with unplanned formal overnight admission into hospital, usually for purpose of investigating and/or treating the AE. Hospitalisation for the treatment of a medical condition that occurs on an “elective” or “scheduled” basis or for a pre-existing condition that did not worsen during the study should not necessarily be regarded as an AE. Complications that occur during the hospitalisation are AEs. If a complication prolongs hospitalisation, the event is an SAE. Emergency room visits

Clinical Study Code No.: CLI-10067AA1-01	Version No.: 6.0
EUDRACT No.: 2022-001079-15	Date: 06 July 2023

that do not result in a formal admission into hospital should be evaluated for one of the other seriousness criteria (e.g., life-threatening; persistent or significant disability or incapacity; medically significant).

- **Results in persistent or significant disability or incapacity**

The term significant disability should be viewed as any situation whereby an AE has a clinically important effect on the subject's physical or psychological well-being to the extent that the subject is unable to function normally.

- **Is a congenital anomaly or birth defect**
- **Is a medically significant adverse event**

This criterion allows for any situations in which important AE/adverse reactions that are not immediately life-threatening or do not result in death or hospitalisation may jeopardise the subject's health or may require intervention to prevent one of the above outcomes.

Examples of such events are: intensive treatment in an emergency room or at home for allergic bronchospasm; blood dyscrasias or convulsions that do not result in hospitalisation; or development of drug dependency or drug abuse.

Medical and scientific judgment should be exercised in deciding whether an event is serious because medically significant.

Any suspected transmission via a medicinal product of an infectious agent is also considered a serious adverse reaction.

A Non-Serious Adverse Event/Non-Serious Adverse Drug Reaction is an AE or ADR that does not meet the criteria listed above for an SAE/serious adverse drug reaction.

10.2 Expectedness

An expected adverse reaction is an adverse reaction, the nature or severity of which is consistent with the applicable reference safety information (included in the IB for CHF10067) otherwise it is considered unexpected.

Reports which add significant information on specificity or severity of a known, already documented serious ADR constitute unexpected events. For example, an event more specific or more severe than described in the reference safety information would be considered as "unexpected". Examples of such events are: (a) acute renal failure as a labelled ADR with a subsequent new report of interstitial nephritis and (b) hepatitis with a first report of fulminant hepatitis.

In the event an exacerbation is interpreted as due to lack of efficacy, it should not be classified as drug related.

Clinical Study Code No.: CLI-10067AA1-01	Version No.: 6.0
EUDRACT No.: 2022-001079-15	Date: 06 July 2023

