1.3 Risk/Benefit Assessment

Subjects in the current study are not expected to experience any health benefit (beyond that of an assessment of their medical status) from participating in the study, since they will be exposed to a single dose of treatment. The risks of participation are primarily those associated with adverse reactions to CHF10067, although there may also be some risks associated with the collection of blood samples and other study procedures. Subjects will be followed at the clinical site and closely monitored throughout the study period. Intravenous doses up to [REDACTED]

[REDACTED] have been safely tested in healthy subjects; therefore, a starting dose of 1000 mg is considered appropriate to be tested in the patient population. Considering the safety profile of CHF10067, the measures in place to assure the subjects' safety, and the expected scientific value, the overall risk/benefit assessment can be considered acceptable for the proposed study. More information about the known and expected benefits and risks associated with CHF10067 may be found in the IB.

This study will be conducted in compliance with the Declaration of Helsinki (1964 and amendments), current International Council on Harmonisation (ICH) E6 Good Clinical Practices (GCP), and all other applicable laws and regulations.

Clinical Study Code No.: CLI-10067AA1-01	Version No.: 6.0
EUDRACT No.: 2022-001079-15	Date: 06 July 2023

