The decision to dose-escalate will be a unanimous decision between the Sponsor, Medical Monitor, and the Coordinating Investigator. If either the Sponsor or the Coordinating Investigator considers stopping of dose escalation to be appropriate, dose escalation will be terminated.

Study drug will be discontinued in any individual subject that experiences a drug-related serious AE (SAE) or any other AE that, in the opinion of the Coordinating Investigator or site Investigator, warrants discontinuation of study drug.

Doses will not be further escalated if:

- Two or more subjects on active drug* experience a possibly drug-related SAE
- Two or more subjects on active drug* experience a severe, possibly drug-related AE lasting for > 24 hours duration
- Four or more subjects on active drug* experience at least moderate, possibly drug-related AE in the same Medical Dictionary for Regulatory Activities (MedDRA) System Organ Class of > 24 hours duration

Clinical Study Code No.: CLI-10067AA1-01	Version No.: 6.0
EUDRACT No.: 2022-001079-15	Date: 06 July 2023

- Despite the above criteria not being met, a pattern of AEs has emerged that leads the Investigator and/or Safety Advisory Committee to believe that dose escalation is not justifiable on safety grounds.

* Unblinding is possible to take an informed decision before stopping the dose escalation, as detailed in the separate charter.

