10.4 Causality Assessment

The following “binary” decision choice will be used by the Investigator to describe the causality assessment:

- Reasonable possibility of a relatedness
- No reasonable possibility of relatedness.

The expression “reasonable possibility of relatedness” is meant to convey, in general, that there are facts (evidence), or arguments meant to suggest a causal relationship.

The Investigator will be asked to consider the following before reaching a decision on causality assessment:

- Time relationship between study drug intake and event’s onset
- Dechallenge (did the event abate after stopping drug?)
- Rechallenge (did the event reappear after reintroduction?)
- Medical history
- Study treatment(s)
- Mechanism of action of the study drug
- Class effects
- Other treatments-concomitant or previous
- Withdrawal of study treatment
- Lack of efficacy/worsening of existing condition
- Erroneous treatment with study medication (or concomitant)
- Protocol related process.

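### Protocol 10.2 fixes the causality answer for an exacerbation read as lack of efficacy; this conflicts with 10.4 and 1.3 and can remove events from relatedness-based counts

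*Protocol*

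**What the plan says.** Protocol 10.2, headed Expectedness, contains one sentence on causality: "In the event an exacerbation is interpreted as due to lack of efficacy, it should not be classified as drug related".

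Protocol 10.4 is the causality section. The investigator makes a binary choice between a reasonable possibility of relatedness and none, after considering twelve listed factors. One of them is "Lack of efficacy/worsening of existing condition". No factor is given a fixed consequence.

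Protocol 1.3 says "Subjects in the current study are not expected to experience any health benefit". Apart from a check of their health, participants gain nothing, and the section gives the reason: "since they will be exposed to a single dose of treatment". The objectives in section 2 are safety and tolerability, PK, immunogenicity and TG2 levels. None is efficacy.

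Protocol 6.2.2.1 lists four grounds for not escalating further. Three are counts that require possible relatedness:

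- The rule on serious events reads "Two or more subjects on active drug* experience a possibly drug-related SAE", so it triggers at a count of two.
- The rule on severe events has the same threshold and adds a minimum duration: "Two or more subjects on active drug* experience a severe, possibly drug-related AE lasting for > 24 hours duration".
- The third rule needs at least four active-arm subjects whose possibly related events are of moderate or worse intensity, fall in one MedDRA System Organ Class and last more than a day.

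The fourth ground is a judgement with no relatedness condition. Its opening is "Despite the above criteria not being met, a pattern of AEs has emerged that leads the Investigator and/or Safety Advisory Committee to believe"; the belief meant is that going to a higher dose could not be defended for safety reasons.

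**The concern.** The sentence in 10.2 turns one consideration from 10.4 into an answer. Once an exacerbation carries the label of lack of efficacy, timing, mechanism and class effects no longer affect the coding. The label also has little basis in this trial: where no benefit is expected from the dose, its absence does not explain an event. The protocol gives no criteria for applying it, and the investigator is blinded.

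Post-dose exacerbations are foreseen, since section 5.2 allows for treating them. Section 1.2 notes that no data in IPF had yet been collected. Acute respiratory worsening is therefore an event whose causality this trial needs to judge without a preset answer. At stake are the outputs and rules that depend on the relatedness code, including the escalation counts.

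**Working it through.** The plan states no power, error rate or stopping probability on this point, so there is no figure of its own to reproduce. The check traces what the relatedness code controls.

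**What happens to an exacerbation coded not related**

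| Rule or output | Source | Effect |
|---|---|---|
| Three count-based escalation criteria | Protocol 6.2.2.1 | Not counted |
| ADR and serious ADR tables (14.3.1.5, 14.3.1.6) | SAP 3.1.2, 9.1 | Left out; an ADR is a TEAE that is related or has a missing relationship |
| Replacement of a subject who discontinues for safety reasons | Protocol 4.4 | The bar on replacement no longer applies |
| SUSAR assessment | Protocol 10.1, 10.10 | Left out, unless the sponsor judges the event related |
| Pattern-of-AEs criterion | Protocol 6.2.2.1 | Still applies |
| TEAE, serious TEAE, grade 3 or 4 and fatal TEAE tables | SAP 3.1.3 | Still included where the event qualifies |
| SAE reporting within 24 hours | Protocol 10.9 | Still required, related or not |

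The SAP has no table of post-dose exacerbations. Its exacerbation tables (14.1.2.3.1 and 14.1.2.3.2) cover history before the study.

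**Leverage of one event.** Each cohort has 6 active subjects, and the first two criteria trigger at 2. If two active subjects have qualifying events and one is recoded, the count is 2 − 1 = 1 and the criterion is not met.

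**Illustration, on assumed inputs only.** Let p be an assumed per-subject risk of an exacerbation that is an SAE, and f an assumed share coded not related because of the sentence. All others are treated as possibly related. With q = p(1 − f), the chance that n active subjects yield at least two counted events is

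P = 1 − (1 − q)^n − n·q·(1 − q)^(n−1)

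For n = 6 and p = 20%:

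- f = 0: 1 − 0.8^6 − 6 × 0.2 × 0.8^5 = 1 − 0.26214 − 0.39322 = 34.5%
- f = 50%, so q = 10%: 1 − 0.9^6 − 6 × 0.1 × 0.9^5 = 1 − 0.53144 − 0.35429 = 11.4%

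| p | n = 6, f = 0 | n = 6, f = 25% | n = 6, f = 50% | n = 12, f = 0 | n = 12, f = 50% |
|---|---|---|---|---|---|
| 5% | 3.3% | 1.9% | 0.9% | 11.8% | 3.5% |
| 10% | 11.4% | 6.9% | 3.3% | 34.1% | 11.8% |
| 20% | 34.5% | 22.4% | 11.4% | 72.5% | 34.1% |
| 30% | 58.0% | 40.6% | 22.4% | 91.5% | 55.7% |

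At f = 100% every entry is 0. The n = 12 columns apply only if counts accumulate over Cohorts A and B, which the text does not say. The f = 0 columns are upper bounds, because some exacerbations would be judged unrelated under 10.4 anyway. The table shows how sensitive a threshold of two is to recoding. It does not predict this trial.

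**The case against.** The strongest reply is that the sentence is conditional. It applies only after an exacerbation has been interpreted as due to lack of efficacy, and that interpretation is itself a causality judgement. An investigator who suspects the drug has not made that interpretation and goes to 10.4. On this view the sections can be read in sequence, and since 1.3 expects no benefit, the label should seldom be used. This stands in part: nothing makes not related the default for exacerbations, so a reader who infers that 10.2 codes all of them that way goes beyond the text. But the sentence still lets one factor settle the outcome where 10.4 asks for all twelve to be weighed, and lack of efficacy does not exclude a drug contribution.

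A second reply is that safeguards remain, and this also stands:

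- The pattern criterion needs no relatedness.
- Escalation needs a unanimous decision, and the sponsor or the coordinating investigator can end it.
- The Safety Advisory Committee receives all available safety assessments (6.2.2.1).
- Section 10.1 lets the sponsor as well as the investigator judge an event an adverse reaction. The sentence in 10.2 exempts neither, however.
- Spirometry, diffusing capacity and oxygen saturation are measured whatever the AE coding.

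These are backstops. They do not restore a pre-specified count.

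A third reply is that an exacerbation, as defined in exclusion criterion 2, requires the absence of other identifiable causes, so an identified drug injury would not be one. That definition is written for eligibility, and an unrecognised drug cause could still be recorded as an exacerbation.

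Finally, qualifying exacerbations may be few. Entry requires three months of stability and no acute exacerbation in the three months before screening, and escalation needs safety data only to Day 14. This is fair, and the documents give no rate with which to settle it.

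**Conclusion.** The conflict between 10.2 and 10.4, and the poor fit with 1.3, are on the face of the protocol. The consequence is a possibility: an exacerbation with a reasonable possibility of relatedness could be coded not related and leave the three count-based criteria, the ADR and serious ADR tables, the replacement rule and, unless the sponsor judges it related, SUSAR assessment. The size is unknown, because neither the exacerbation risk nor the share so coded can be taken from the documents.

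Three stronger readings are tempting and not supported:

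- **That exacerbations disappear from the safety evaluation.** They stay in the causality-free TEAE outputs and in SAE reporting.
- **That the primary safety result is biased in the drug's favour.** The sentence applies to both arms under blinding, and only the relatedness-based outputs and counts can be understated.
- **That ADR incidence would read 0/6 instead of 2/6 (33%).** That example assumes two events that are both possibly related and labelled lack of efficacy, so it assumes its own result.

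Severity: should-fix. The wording touches the primary objective and the escalation counts and is cheap to correct, but other routes to detection and stopping remain.

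**What to change.** Reconcile 10.2 and 10.4 by deleting the sentence from 10.2. Every post-dose exacerbation is then assessed under 10.4 like any other AE, with no default answer in either direction. A rule that lack of efficacy can never support a finding of not related should not be added, because that would replace one preset answer with another.

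Ask sites to re-assess any exacerbation already coded under the sentence, while still blinded and before database lock. If the blind is already broken, keep the coding as recorded and add a listing of all post-dose exacerbations by treatment with their causality. Changing causality after unblinding would bias the ADR tables.

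The cost is one deleted sentence in an amendment, a note to sites and, if needed, one listing. The downside is that a few disease-related exacerbations may be recorded as possibly related and need review.

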10.3 Intensity of Adverse Event

For the classification of AEs severity (except for immediate hypersensitivity reactions severity, see below), the Common Terminology Criteria for Adverse Events (CTCAE) [23] will be used:

- Grade 1 Mild; asymptomatic or mild symptoms; clinical or diagnostic observations only; intervention not indicated.
- Grade 2 Moderate; minimal, local, or noninvasive intervention indicated; limiting age-appropriate instrumental Activities of Daily Living (ADL)*.
- Grade 3 Severe or medically significant but not immediately life-threatening; hospitalization or prolongation of hospitalization indicated; disabling; limiting self-care Activities of Daily Living**.
- Grade 4 Life-threatening consequences; urgent intervention indicated.
- Grade 5 Death related to AE.

*Instrumental ADL refer to preparing meals, shopping for groceries or clothes, using the telephone, managing money, etc.

**Self-care ADL refer to bathing, dressing and undressing, feeding self, using the toilet, taking medications, and not bedridden.

In order to guarantee objectivity and consistency in the evaluation of AEs (including classification of severity), the proposed guidance should be followed in alignment with best medical practice.

Laboratory abnormalities and other clinical assessments (e.g., 12-lead ECG) will be reported as AEs if judged by the Investigator as being clinically significant.

In case of laboratory evaluations or other clinical assessments (e.g., 12 -lead ECG) not listed in the CTCAE grading table, the AE severity will be judged by the Investigator based on the local ranges.

Taking into consideration the disease examined in the current study, it should be acknowledged that the guidance may not always be applied. Therefore, although the guidance should be followed, whenever possible, in order to ensure an accurate and objective evaluation of the AEs, the final decision on the severity classification remains the responsibility of the Investigator.

For the specific classification of severity and management of immediate hypersensitivity reactions, refer to [Section 7.2.2.5.1](#).

Clinical Study Code No.: CLI-10067AA1-01	Version No.: 6.0
EUDRACT No.: 2022-001079-15	Date: 06 July 2023

